16.4 Listings

Number	Title	Population	Early Stop	Programming notes ¹
16.2.1.1	Reasons for Screen Failure	Enrolled	Yes	
16.2.1.2	Reasons for Discontinuation from Study Drug	ITT	Yes	
16.2.1.3	Reasons for Withdrawal from the Study	ITT	Yes	
16.2.1.4	Participants for Whom the Blind Was Broken	ITT	Yes	
16.2.1.5	Planned and Actual Treatments	ITT	Yes	
16.2.2	Protocol Deviations	ITT	Yes	
16.2.3	Participants Excluded from Any Population	Enrolled	Yes	
16.2.4.1	Demographics	ITT	Yes	DMC-Unblinded
16.2.4.2	Smoking Status	ITT	Yes	DMC-Unblinded
16.2.4.3	Baseline Disease Characteristics	ITT	Yes	DMC-Unblinded
16.2.4.4	COVID-19 Comorbidities	ITT	Yes	
16.2.4.5	Other Medical History	ITT	Yes	
16.2.4.6	Prior Medications	ITT	Yes	
16.2.4.7	Concomitant Medications	ITT	Yes	DMC-Unblinded
16.2.4.8	Concomitant Procedures	ITT	Yes	
16.2.4.9	Compliance with Study Treatment	Safety	Yes	
16.2.4.10	Compliance with Daily Diary Completion After Discharge	ITT	Yes	
16.2.5	Exposure to Study Treatment	Safety	Yes	DMC-Unblinded
16.2.6.1	Oxygen Saturation	ITT	Yes	

Number	Title	Population	Early Stop	Programming notes ¹
16.2.6.2	WHO OSCI Score	ITT	Yes	DMC-Unblinded
16.2.6.3	Overall Survival	ITT	Yes	
16.2.6.4	Intubation and Mechanical Ventilation Free Survival	ITT	Yes	
16.2.6.5	Time to Discharge	ITT	Yes	
16.2.6.6	Time to SpO ₂ ≥94% on Room Air Without Further Requirement for Oxygen Therapy	ITT	Yes	
16.2.6.7	Time to Recovery from Onset of Symptoms	ITT	Yes	
16.2.6.8	Temperature Data	ITT	Yes	
16.2.6.9	Oxygen Therapy	ITT	Yes	
16.2.6.10	Number of Days Requiring Oxygen Therapy and Number of Days with Pyrexia >=38 C	ITT	Yes	
16.2.6.11	Daily Diary	ITT	Yes	
16.2.6.12	Cytokine Levels	ITT		
16.2.6.13	Inflammatory Response Markers	ITT	Yes	
16.2.7.1	Adverse Events	Safety	Yes	DMC-Unblinded
16.2.7.2	Serious Adverse Events	Safety	Yes	DMC-Unblinded
16.2.7.3	Adverse Events Leading to Permanent Discontinuation from Study Drug or Withdrawal from the Study	Safety	Yes	DMC-Unblinded
16.2.7.4	Fatal Adverse Events	Safety	Yes	DMC-Unblinded
16.2.7.5	Adverse Events of Special Interest	Safety	Yes	DMC-Unblinded
16.2.8.1	Hematology Parameters	Safety	Yes	
16.2.8.2	Hematology Parameters for Participants with at Least One PCI Value	Safety	Yes	DMC-Unblinded
16.2.8.3	Clinical Chemistry Parameters	Safety	Yes	
16.2.8.4	Clinical Chemistry Parameters for Participants with at Least One PCI Value	Safety	Yes	DMC-Unblinded
16.2.9.1	Vitals Signs	Safety	Yes	
16.2.9.2	Vitals Signs for Participants with at Least One PCI Value	Safety	Yes	DMC-Unblinded
16.2.10	Physical Examination at Screening	Safety	Yes	
16.2.11	Female Fertility Status and Pregnancy Test Results	Safety	Yes	

Number	Title	Population	Early Stop	Programming notes ¹
16.2.12.1	Presence of EDP1815 in Plasma Samples	Safety		
16.2.12.2	Presence of EDP1815 in Stool Samples	Safety		

17 Appendix 2: MedDRA Internationally Agreed Order for System Organ Class

The internationally agreed SOC order to be used for medical history and AE summary tables is provided in **Table 15**.

Table 15 MedDRA Internationally Agreed SOC Order

Order Number	System Organ Class
1	Infections and infestations
2	Neoplasms benign, malignant and unspecified (incl cysts and polyps)
3	Blood and lymphatic system disorders
4	Immune system disorders
5	Endocrine disorders
6	Metabolism and nutrition disorders
7	Psychiatric disorders
8	Nervous system disorders
9	Eye disorders
10	Ear and labyrinth disorders
11	Cardiac disorders
12	Vascular disorders
13	Respiratory, thoracic and mediastinal disorders
14	Gastrointestinal disorders
15	Hepatobiliary disorders
16	Skin and subcutaneous tissue disorders
17	Musculoskeletal and connective tissue disorders
18	Renal and urinary disorders
19	Pregnancy, puerperium and perinatal conditions
20	Reproductive system and breast disorders
21	Congenital, familial and genetic disorders
22	General disorders and administration site conditions
23	Investigations
24	Injury, poisoning and procedural complications
25	Surgical and medical procedures
26	Social circumstances
27	Product issues

18 Cytokines and Inflammatory Response Markers

Table 16 Biomarker Parameters and Units

Category	Parameter	Unit
Cytokines	EGF	TBC
	Eotaxin/CCL11	TBC
	FGF-2	TBC
	Flt3 Ligand	TBC
	Fractalkine/CX3CL1	TBC
	G-CSF	TBC
	GM-CSF	TBC
	GRO α	TBC
	IFN α 2	TBC
	IFN γ	TBC
	IL-12 (p70)	TBC
	IL-13	TBC
	IL-15	TBC
	IL-17A/CTLA8	TBC
	IL-17E/IL-25	TBC
	IL-17F	TBC
	IL-18	TBC
	IL-1RA	TBC
	IL-1 α	TBC
	IL-1 β	TBC
	IL-27	TBC
	IL-3	TBC
	IL-4	TBC
	IL-5	TBC
	IL-6	TBC
	IL-7	TBC
	IL-8/CXCL8	TBC
	IL-9	TBC
	IP-10/CXCL10	TBC
	M-CSF	TBC
	MDC/CCL22	TBC
	MIG/CXCL9	TBC
	MIP-1 α /CCL3	TBC
	MIP-1 β /CCL4	TBC
	PDGF-AA	TBC
	PDGF-AB/BB	TBC
	RANTES/CCL5	TBC

Category	Parameter	Unit
	sCD40L	TBC
	TGF α	TBC
	TNF α	TBC
Inflammatory Markers	D-Dimer	ng/mL
	Ferritin	ng/mL
	Troponin I	ng/mL
	C-reactive protein	mg/dL
	Neutrophil/Lymphocyte Ratio	Fraction of 1

19 Appendix 3: Safety Laboratory Evaluations

Table 17 Safety Laboratory Parameters and Units

Category	Parameter	Unit	PCI Criteria	
			Low	High
Hematology	Hemoglobin	g/dL	<10 ≥2 decrease from BL	>2 increase from BL
	Hematocrit	%		
	Red blood cell count	10 ⁶ /uL		
	White blood cell count	10 ³ /uL	<3	
	Platelets	10 ³ /uL	<75	
	Mean Corpuscular Volume	fL		
	Mean Corpuscular Hemoglobin	pg		
	Mean Corpuscular Hemoglobin Concentration	g/dL		
	Absolute neutrophils	10 ³ /uL	<1.5	
	Absolute lymphocytes	10 ³ /uL	<0.5	>4
	Absolute monocytes	10 ³ /uL		
	Absolute eosinophils	10 ³ /uL		
	Absolute basophils	10 ³ /uL		
	Relative neutrophils	%		
	Relative lymphocytes	%		
	Relative monocytes	%		
	Relative eosinophils	%		
	Relative basophils	%		
Chemistry	Aspartate aminotransferase	IU/L		>3xULN if BL was normal, <3xBL if BL was above ULN
	Alanine aminotransferase	IU/L		>3xULN if BL was normal, <3xBL if BL was above ULN
	Lactate dehydrogenase	IU/L		
	Creatinine	mg/dL		>1.5xULN >1.5xBL
	Potassium	mmol/L		>5.5
	Sodium	mmol/L	<125	>150
	Urea	mg/dL		

Note: If local lab provides both absolute and relative differentials, only absolute differentials should be completed on the CRF and relative differentials should be marked as not done. If relative differentials only are provided these will be converted to absolute values in the analysis data sets as described in [Section 5.3.4.3](#).

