7.4.2 Planned Schedule of Interim Analyses

Interim analyses are planned after 10, 20, 30, 40 and 60 participants have completed 7 days follow-up after their last dose (Day 21 for participants who complete dosing as scheduled).

At all interim analyses, the DMC will review safety and study disposition data to assess the safety of the interventions and to monitor the overall conduct of the study. Safety review will focus on the number and details of severe and serious adverse events, gastrointestinal (GI) events of any grade and laboratory data which meets the criteria for potentially clinically important (PCI).

At the second interim, after 20 participants have completed 7 days of follow-up after their last dose, the DMC will also specifically address the question of recruitment can be opened to participants aged >65 years.

At the final interim, after 60 participants have completed 7 days of follow-up after their last dose, the DMC will also review the efficacy data in order to make a recommendation on whether recruitment should be extended to a further 40 participants.

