10.4 Clinical Laboratory Evaluations

Local laboratory data will be used for all safety laboratory evaluations. Blood samples for safety laboratory evaluations will be collected at Baseline, Day 4 and Day 7. [Table 17](#) shows the parameters which will be collected and the units in which they will be supplied.

Laboratory data (hematology and chemistry parameters) will be summarized by treatment and visit. Changes from baseline at Day 4 and Day 7 will also be summarized.

Relative differentials (neutrophils, lymphocytes, monocytes, eosinophils and basophils) will be converted to absolute values as described in [Section 5.3.4.3](#).

The number and percentage of participants showing shifts from baseline to worst-case post-baseline with respect to the normal ranges will also be summarized for each parameter. Categories will be:

- Low
- Normal
- High

The determination of worst-case post-baseline will consider both scheduled (Day 4 and Day 7) and any unscheduled assessments which occur after the first dose of study treatment. Percentages will use the number of participants with at least one post-baseline assessment available. If the baseline value is missing it will be assumed to be normal for this summary. Worst-case can be either High or Low and if a participant has post-Baseline values both above and below the normal range then they will be counted in both relevant categories.

Safety laboratory values are also flagged for potentially clinically important (PCI) values if they meet any of the criteria for Grade 2 or higher events according to CTCAE V5.0 with the exception of lymphocytes where the lower limit for grade 3 is used as COVID-19 cases lymphopenia in most patients. The PCI criteria are listed in [Table 17](#). The number and percentage of participants showing shifts from baseline to worst-case post-baseline with respect to PCI criteria will be summarized for all parameters where PCI criteria have been defined. Categories will be:

- Low
- Within range
- High

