The determination of worst-case post-baseline will consider both scheduled (Day 4 and Day 7) and any unscheduled assessments which occur after the first dose of study treatment. Percentages will use the number of participants with at least one post-baseline assessment available. If the baseline value is missing it will be assumed to be within range for this summary. Worst-case can be either High or Low and if a participant has post-Baseline values both above and below the PCI criteria then they will be counted in both relevant categories.

Safety laboratory data will be listed by participant, including changes from baseline, normal ranges and flags for measurements outside the normal range and flags for meeting PCI criteria. In addition, for participants who meet at least one PCI criteria, all values within the laboratory type (hematology or clinical chemistry) will be listed separately.

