16.3 Safety

16.3.1 Tables

Number	Title	Population	Early Stop	Programming notes ¹
14.3.1.1.1	Summary of All TEAEs by System Organ Class and Preferred Term	Safety	Yes	DMC-Unblinded
14.3.1.1.2	Summary of Treatment Phase TEAEs by System Organ Class and Preferred Term	Safety	Yes	DMC-Unblinded
14.3.1.1.3	Summary of Follow-up Phase TEAEs by System Organ Class and Preferred Term	Safety	Yes	DMC-Unblinded
14.3.1.1.4	Summary of All TEAEs by Age Group, System Organ Class and Preferred Term	Safety		DMC-Safety Only produced if participants aged >65 are permitted to enter the study
14.3.1.2	Summary of Treatment-Related TEAEs by System Organ Class and Preferred Term	Safety	Yes	
14.3.2.1	Summary of Serious TEAEs by System Organ Class and Preferred Term	Safety	Yes	DMC-Unblinded
14.3.2.2	Summary of TEAEs Leading to Permanent Discontinuation from Study Drug by System Organ Class and Preferred Term	Safety	Yes	
14.3.2.3	Summary of TEAEs Leading to Withdrawal from the Study by System Organ Class and Preferred Term	Safety	Yes	
14.3.2.4	Summary of Fatal TEAEs by System Organ Class and Preferred Term	Safety	Yes	

Number	Title	Population	Early Stop	Programming notes ¹
14.3.2.5.1	Summary of TEAEs of Special Interest by Preferred Term and CTCAE Grade	Safety	Yes	DMC-Unblinded
14.3.2.5.2	Summary of TEAEs of Special Interest by Preferred Term and Relationship to Study Drug	Safety	Yes	DMC-Unblinded
14.3.4.1.1	Summary of Change from Baseline in Hematology	Safety	Yes	
14.3.4.1.2	Summary of Shifts from Baseline to Worst-case Post-Baseline with Respect to the Normal Range in Hematology	Safety	Yes	DMC-Unblinded
14.3.4.1.3	Summary of Shifts from Baseline to Worst-case Post-Baseline with Respect to the PCI Criteria in Hematology	Safety	Yes	DMC-Unblinded
14.3.4.1.4	Summary of Shifts from Baseline to Worst-case Post-Baseline with Respect to the PCI Criteria in Hematology, by Age Group	Safety		DMC-Safety Only produced if participants aged >65 are permitted to enter the study
14.3.4.2.1	Summary of Change from Baseline in Clinical Chemistry	Safety	Yes	
14.3.4.2.2	Summary of Shifts from Baseline to Worst-case Post-Baseline with Respect to the Normal Range in Clinical Chemistry	Safety	Yes	DMC-Unblinded
14.3.4.2.3	Summary of Shifts from Baseline to Worst-case Post-Baseline with Respect to the PCI Criteria in Clinical Chemistry	Safety	Yes	DMC-Unblinded

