14.3.4.2.4	Summary of Shifts from Baseline to Worst-case Post-Baseline with Respect to the PCI Criteria in Clinical Chemistry, by Age Group	Safety		DMC-Safety Only produced if participants aged >65 are permitted to enter the study
14.3.5.1	Summary of Change from Baseline in Vital Signs	Safety	Yes	
14.3.5.2	Summary of Shifts from Baseline to Worst-case Post-Baseline with Respect to the PCI Criteria in Vital Signs	Safety	Yes	DMC-Unblinded

Number	Title	Population	Early Stop	Programming notes ¹
14.3.5.3	Summary of Shifts from Baseline to Worst-case Post-Baseline with Respect to the PCI Criteria in Vital Signs, by Age Group	Safety		DMC-Safety Only produced if participants aged >65 are permitted to enter the study

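### SAP Table 17 reverses the AST/ALT High criterion when baseline is above ULN, so the liver PCI flags sent to the DMC would be inverted for that group

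*SAP*

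**What the plan says.** SAP Section 10.4 sets the basis for laboratory flags: "Safety laboratory values are also flagged for potentially clinically important (PCI) values if they meet any of the criteria for Grade 2 or higher" under CTCAE v5.0. Lymphocytes are the only stated exception, and the reader is sent to Table 17 for the criteria. In the High column of Table 17 the AST and ALT rows carry the same entry: ">3xULN if BL was normal, <3xBL if BL was above ULN". The creatinine row, also partly relative to baseline, reads ">1.5xULN >1.5xBL".

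The flags are used in these outputs:

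- Shift table 14.3.4.2.3, "Summary of Shifts from Baseline to Worst-case Post-Baseline with Respect to the PCI Criteria in Clinical Chemistry", and its age-group version 14.3.4.2.4, which is produced only if participants over 65 are admitted.
- Listing 16.2.8.4. Section 10.4 says that "for participants who meet at least one PCI criteria, all values within the laboratory type (hematology or clinical chemistry) will be listed separately".
- The full chemistry listing 16.2.8.3, which carries the PCI flags but is not marked for the DMC.

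Appendix 1 of the SAP marks 14.3.4.2.3 and 16.2.8.4 as unblinded outputs for every DMC meeting. Section 7.4.2 lists "laboratory data which meets the criteria for potentially clinically important (PCI") among the things the DMC safety review concentrates on.

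On vital signs, Section 10.5.1 plans daily summaries over Days 1-14. It then defines the worst post-baseline value from scheduled readings on Days 4 and 7 plus any unscheduled ones. The protocol's Schedule of Activities has vital signs taken every day in hospital.

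**The concern.** A High flag is meant to mark a rise. As printed, the baseline-relative half of the AST/ALT rule is met by any value that has not risen to three times baseline, and it stops being met once the value reaches that level. A DMC member reading the chemistry PCI shift table would see recovering or unchanged participants counted as High, and a sustained large rise counted as within range.

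The affected group can be enrolled. Protocol Section 5.2, criterion 9, excludes known significant liver disease with ALT or AST at 5.0 x ULN or more, so lesser elevations at baseline are eligible.

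For vital signs, a blood-pressure excursion on a scheduled day other than Day 4 or Day 7 would not reach shift tables 14.3.5.2 and 14.3.5.3, although the reading was planned and collected.

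**Working it through.** **Direction of the sign, from the documents.** The other entries in the High column are hemoglobin (more than 2 above baseline), lymphocytes (>4), creatinine (">1.5xULN >1.5xBL"), potassium (>5.5) and sodium (>150). All use greater-than. The first half of the AST/ALT cell also uses greater-than, and the reversed sign appears in both rows, so a fault in reading the PDF is unlikely. No other part of the SAP gives a different AST/ALT rule.

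**Effect on single values.** Write BL for baseline and v for a follow-up value.

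- BL normal: flag if v > 3 x ULN (not in dispute).
- BL above ULN, as printed: flag if v < 3 x BL.
- BL above ULN, sign reversed: flag if v > 3 x BL.

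Take an assumed ULN of 40 and BL of 60, so 3 x BL = 180. As printed, 30, 45, 60, 120 and 179 are flagged High; 181, 200 and 400 are not. With the sign reversed each of these flags switches. For BL above ULN the result depends only on v/BL, so the choice of 40 and 60 does not matter.

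Over a grid of BL from 41 to 199 and v from 5 to 2000 (159 x 1996 = 317,364 points), the two versions agree at 159 points, all at v exactly equal to 3 x BL. For BL from 5 to 40 (36 x 1996 = 71,856 points) they agree everywhere.

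**Effect on the shift table.** Let each of Day 4 and Day 7 be 120 (below the cut-off) or 200 (above it). Section 10.4 states "If the baseline value is missing it will be assumed to be within range for this summary", which implies that a baseline value that is present is itself classified. Under the printed rule 60 < 180, so baseline counts as High.

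| Day 4, Day 7 | Intended | Printed, baseline classified | Printed, baseline held within range |
|---|---|---|---|
| 120, 120 | Within to Within | High to High | Within to High |
| 120, 200 | Within to High | High to High | Within to High |
| 200, 120 | Within to High | High to High | Within to High |
| 200, 200 | Within to High | High to Within | Within to Within |

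With baseline classified, 4 of 4 patterns are in the wrong cell, and no rise cannot be told from a rise at one visit. With baseline held within range, 2 of 4 are wrong, and a participant above 3 x BL at both visits carries no AST or ALT flag.

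**Vital signs.** Assume a full inpatient stay and no unscheduled readings, and count Days 2-14. Day 1 is left out because Section 5.3.1.2 treats untimed Day 1 data as pre-dose. The positions of an excursion that avoid both Day 4 and Day 7 are:

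- One day: 13 - 2 = 11 of 13 (85%).
- Three days: start days run from 2 to 12. Starts 2-4 include Day 4 and starts 5-7 include Day 7, so starts 8-12 are missed: 5 of 11 (45%).
- Five days: start days run from 2 to 10, and starts 8-10 are missed: 3 of 9 (33%).
- Stay ending on Day 7: 4 of 6 (67%) for one day, 0 of 4 for three days.

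**The case against.** The strongest reply is that this is a visible typing error. Section 10.4 states the governing principle in words, a less-than sign in a High column contradicts it, and a careful programmer would probably query it. The documents contain no code, so the outputs are wrong only if Table 17 is followed literally. That condition stands. Even so, Table 17 is where Section 10.4 sends the programmer for the thresholds.

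Second, the literal rule mostly over-flags. Anyone with a raised baseline and at least one post-baseline value below 3 x BL enters listing 16.2.8.4, where all their chemistry values can be read. A participant drops out only if baseline is unflagged, every later value is at or above 3 x BL, and no other chemistry parameter is flagged. This limits the harm to the DMC. It does not repair the shift table.

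Third, there are other safeguards. The DMC also receives normal-range shift table 14.3.4.2.2 and the adverse event outputs, investigators must review laboratory reports, and no stopping rule refers to a PCI flag. These help only partly. Someone already above ULN who rises further stays High to High in the normal-range table. Non-serious Grade 1-2 events other than the named gastrointestinal ones are not entered in the CRF (Protocol Section 8.3).

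On vital signs, the Day 4 and Day 7 wording looks carried over from the laboratory section. The fractions above count positions and are not expected miss rates. The PCI criteria cover only systolic and diastolic pressure, and DMC listing 16.2.9.2 shows every reading for anyone with a PCI value. All of this is fair and keeps the point minor.

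**Conclusion.** The criterion is wrong as written and should be fixed. For participants with AST or ALT above ULN at baseline, the printed rule gives the opposite of the intended flag at every value except exactly 3 x BL. It misplaces either 4 of 4 or 2 of 4 shift patterns, depending on how baseline is classified. These patterns are not equally likely, so the counts are not error rates.

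The conclusion assumes that outputs are programmed from Table 17 as printed. The number of participants affected cannot be stated, because the documents give no frequency of raised baseline values. The multiple of 3 is taken as printed; CTCAE is not among the documents and was not checked. The error would carry into the final-analysis versions of the outputs as well as the DMC ones. Flags for normal baselines, the normal-range shift tables, the adverse event tables and all efficacy analyses are unaffected.

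The vital-signs wording is a lesser but genuine gap, confined to the shift tables.

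**What to change.** - **Table 17, AST and ALT rows:** reverse the second inequality so that, when baseline is above ULN, High means greater than 3 x BL. When making the change, confirm both rows against the CTCAE v5.0 criteria that Section 10.4 cites.
- **Programs:** check the matching lines and re-run any chemistry PCI output already produced from the printed rule (14.3.4.2.3, 14.3.4.2.4, 16.2.8.4, and the flags in 16.2.8.3).
- **Section 10.5.1:** define the worst case for vital signs over all scheduled and unscheduled assessments after the first dose. This also covers participants still in hospital after Day 14.

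The cost is one character in each of two rows, one phrase in Section 10.5.1 and the corresponding program lines. No new data are needed.
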